2.7.1.1 Adverse events of special interest / grouping of AEs

The following treatment emergent adverse event of special interest will be summarized.

- Angioedema
- Long term effects on growth bone growth and mineralisation in the pediatric population
- Cognitive impairment
- Embryo-fetal toxicity or lethality
- Hepatotoxicity
- Hyperkalaemia
- Hypotension
- Neonatal or infantile toxicity through exposure from breast milk
- Renal impairment
- Statin drug-drug interaction

The definitions of these events will be defined in the electronic Case Retrieval Strategy (eCRS, ID: 6511 LCZ696 Hf (adult and pediatric)).

For each risk, the following analyses will be conducted.

- Numbers and percentages of patients with any TEAE within the risk category (or SOC/PT within risk category) by risk category, SOC, PT and maximum severity.
- Listing of Subject ID per risk.

In addition, the MedDRA coding definitions for each risk on the eCRS used to analysis will be listed regardless of the presence or absence of applicable patients.

The SAF will be used for the above analyses.

2.7.2 Deaths

Death during the treatment period and the primary cause of death will be summarized using frequencies and percentages.

A listing of all deaths and heart transplant will also be provided.

The SAF will be used for the above analyses.

2.7.3 Laboratory data

A listing of laboratory data collected in eCRF (i.e. Serum sodium, potassium, creatinine, and estimated Glomerular Filtration Rate (eGFR)) will be provided for the following information by each test item.

- Subject ID
- Date of Study Treatment start
- Collection date (Treatment day)

Displays the collection date entered on CRF or imputed and corresponding Treatment day (the number of days from the date of treatment start).

- Test name
- Test value

Displays the value converted to SI units.

- SI Unit
- Normal range

Displays the normal range converted to SI units.

• Abnormality (H/L)

Displays 'H' if the test value is above the upper limit of the normal range, 'L' if the test value is below the lower limit, otherwise leave blank.

The SAF will be used for the above analyses.

2.7.4 Other safety data

2.7.4.1 ECG and cardiac imaging data

Not applicable

2.7.4.2 Vital signs

Descriptive statistics of vital signs (pulse rate (PR), systolic blood pressure (SBP), diastolic blood pressure (DBP)) for test values and the number of patients and percentages with clinically notable vital signs during the treatment period will be provided by visit (Day1, M6, EOS). These by-visit summaries will only include scheduled assessments. If the timing of EOS and Visit M6

overlaps and two visits are made simultaneously, the data will be used for both EOS and Visit M6. The window of Visit M6 is defined as ± 1 month of the scheduled visit date (day183 ± 30).

Criteria of clinically notable vital signs are shown in the Table 2-1.

Table 2-1 Criteria for clinically notable vital signs

Age	PR [min-1]	SBP [mmHg]	DBP [mmHg]
1- <3 years	<60, >120	<76, >115	<45, >75
3- <6 years	<55, >120	<82, >120	<50, >80
6- <12 years	<50, >105	<90, >130	<50, >80
≥12 years	<45, >95	<90, >145	<55, >90

In addition, all vital signs data collected in eCRF (including unscheduled assessments) will be listed for the following information.

- Subject ID
- Date of Study Treatment start
- Collection date (Treatment day, Visit name)

Displays the collection date entered on CRF or imputed, corresponding Treatment day (the number of days from the date of treatment start) and Visit name.

- Test name
- Test value
- Unit
- Clinically notable vital signs

Displays 'Yes' if the criteria of clinically notable vital signs is met.

The SAF will be used for the above analyses.

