As per Section 4.5, during a public health emergency as declared by local or regional authorities i.e. pandemic, epidemic or natural disaster that limits or prevents on-site study visits, alternative methods of providing continuing care may be implemented by the Investigator as the situation dictates. If allowable by a local health authority, national and local regulations and depending on operational capabilities, phone calls, virtual contacts (e.g. tele consultation) or visits by site staff/ off-site healthcare professional(s) staff to the participant's home, can replace on-site study visits, for the duration of the disruption until it is safe for the participant to visit the site again. If the Investigator delegates tasks to an off-site healthcare professional, the Investigator must ensure the individual(s) is/are qualified and appropriately trained to perform assigned duties. The Investigator must oversee their conduct and remain responsible for the evaluation of the data collected.

Table 1-2 Assessment Schedule

Period			Treatment		
Visit name	Day1#.1	M3 †	M6*	UNS	EOS2
Day/ Month	Day 1	Mo 3	Mo 6	-	-
Obtain Informed Consent (parent (s)- legal guardian (s)/consent-assent (patient, as applicable) ³	х				
Inclusion/ Exclusion	Х				
Demographics/ Medical histories	Х				
Pediatric Heart Failure History	Х				
Physical Examination	s		s	s	S
Vital Signs (BP and pulse)	X 5		Х	Х	Х
Height ⁴	X 5		S	(S)	Х
Weight	X 5		Х	Х	Х
Laboratory assessments (locally) ⁶			Х	(X)	Х
Serum/Urine Pregnancy test (locally) 7			S (Urine)	S (Urine)	S (Serum)
AEs/SAEs	Х	Х	Х	Х	Х
Concomitant medication/ Non-drug therapies	х	х	х	х	х
Dosage Administration Record	Х	Х	Х	(X)	Х
Study Medication Compliance	S		S	(S)	S
Dispense Study Medications	s	S	S	(S)	

UNS= Unscheduled visit, EOS= End of study visit

- X: Assessment to be recorded in the clinical database or received electronically from a vendor
- S: Assessment to be recorded in the source documentation only
- (X) / (S) = parentheses indicate that this is an optional assessment
- # Visit Day1 is the same day as Visit 599 (EOS visit) of PANORAMA-HF OLE (CLCZ696B2319E1) study
- † Visit M3 is a telephone visit.
- * If the trial is extended, Visits M9, M12 to be performed at the same intervals and with same measurements as at Visits M3 and M6, respectively.

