9.5 Exploratory endpoint(s)/estimand(s) analysis

Not applicable. There are no exploratory endpoints.

9.6 (Other) Safety analyses

The following adverse events will be summarized by primary system organ class, and preferred term as appropriate using numbers and percentages of patients with at least one adverse event in the corresponding class.

- Any serious adverse event (treatment emergent or not)
- Treatment emergent adverse event (TEAE*)
- Treatment emergent serious adverse event
- Treatment emergent adverse event of special interest, i.e. events of important identified risks and important potential risks defined in the Risk Management Plan (RMP)

Descriptive statistics of vital signs (raw values) and the number of patients and percentages with clinically notable vital signs during the treatment period will be provided by visit (Day1, M3, M6, EOS). Criteria of clinically notable vital signs are given in the Appendix 3 Table 10-2.

Descriptive statistics (raw values) will be provided for weight, height, BMI, age adjusted percentile for weight and height, and z-score for height by visit.

BMI will be calculated as weight (kg) / height² (m²) using the collected height and weight at each visit.

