2.1.1 General definitions

- The study treatment is sacubitril/valsartan.
- The date of first administration of study treatment during this study is the day of the first non-zero dose of sacubitril/valsartan after patient is enrolled in CLCZ696B2319E2 study.
- The date of last administration of study treatment is the day of the last non-zero dose of sacubitril/valsartan.
- The study period starts with the date of the signature on informed consent (Visit Day 1, the same day as Visit 599 (EOS visit) of PANORAMA-HF OLE study) and ends with the date of end-of-study or premature study discontinuation visit (Visit EOS).
- The treatment period starts with the date of first administration of study treatment in CLCZ696B2319E2 study and ends with the date of treatment disposition. In the case that no EOS visit is undertaken (e.g., because the participant died or withdrew from the study without such a visit), the treatment period ends with the death/withdrawal date, or the last dose taken.
- Baseline is defined as the variable on the date of Visit Day 1 regardless of whether the study treatment is administered on Visit Day 1.
- Study day is defined as actual date date of Visit Day1 + 1

- Treatment day is defined as actual date the date of first administration of study treatment + 1
- Each scheduled visit date is defined using the study day as follows:
 - Visit M3 = day 91
 - Visit M6 = day 183

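### SAP 2.7.4.2 counts clinically notable vital signs only at scheduled Day1, M6 and EOS visits, so a notable value seen only at an unscheduled visit is listed but enters no notable-value count (minor)

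*SAP*

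**What the plan says.** SAP 2.7.4.2 plans descriptive statistics for pulse and blood pressure, and the number and percentage of patients with "clinically notable vital signs during the treatment period will be provided by visit (Day1, M6, EOS"). It then limits both displays: "These by-visit summaries will only include scheduled assessments". A separate listing is complete: "all vital signs data collected in eCRF (including unscheduled assessments) will be listed for the following information". Each record that meets Table 2-1 is marked Yes there.

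Protocol 9.6 plans the same analysis, also by named visit: "number of patients and percentages with clinically notable vital signs during the treatment period will be provided by visit (Day1, M3, M6, EOS"). It has no sentence about scheduled assessments.

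Protocol Table 1-2 marks blood pressure and pulse at unscheduled visits with a plain X. In the table key, "parentheses indicate that this is an optional assessment", and laboratory tests at the same visit do carry parentheses. Vital signs at unscheduled visits are therefore required in the database. For a longer study, "If the trial is extended, Visits M9, M12 to be performed at the same intervals", with M12 repeating the on-site M6 measurements. The last scheduled date that SAP 2.1.1 defines is "Visit M6 = day 183".

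**The concern.** The sole objective of the study is to collect safety information in at most 8 patients. A natural question is how many of them had a notable blood pressure or pulse at any time on treatment, and no planned table answers it. The by-visit rows cannot be added up, because one patient may appear in several of them. They also leave out the visits that Protocol 6.4.1 sets aside for re-checking safety parameters and changing dose level, where a low reading is plausible. The reader would have to count flagged patients in the listing by hand.

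**Working it through.** The plan states no figure for this point, so the check is mainly a comparison of texts.

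1. **Which post-Day1 assessments can be counted.** Day1 values come from Visit 599 of the preceding study (Table 1-2, note 5). M3 is a telephone visit without vital signs, so its absence from the SAP list loses nothing. That leaves M6 and EOS, which are one assessment if the two visits coincide.

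2. **Whether a later visit could fall into the M6 row.** The M6 window is day 183 ± 30, that is day 153 to day 213. M6 lies 182 days after Day1, so M12 at the same interval falls near day 2 × 182 + 1 = 365, well outside the window. A non-EOS visit at M12 or later has no row.

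3. **Whether there is an overall count.** The words about the treatment period qualify the by-visit count. No any-time or worst-value row is specified.

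4. **Whether the AE tables fill the gap.** Under Protocol 8.6.1 an abnormal result is an AE only if it causes signs or symptoms, is clinically significant or needs therapy. The hypotension group in SAP 2.7.1.1 counts treatment-emergent AEs only. The thresholds also differ. An SBP of 86 mmHg at age 6 is notable in SAP Table 2-1 (below 90 for ages 6 to under 12). It is nevertheless above the 82 mmHg in Protocol Table 10-5 that the blood pressure criterion of Table 6-2 uses. Such a reading need not become an AE, and if seen only at an unscheduled visit it would enter no count.

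5. **Scale.** If 8 patients are in the Safety Set, one patient with a notable value only at an uncounted visit changes an any-time percentage by 1/8 = 12.5 points.

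6. **Reach of the table.** The share of one patient's post-Day1 assessments that has a row is c/(m + u). Here m is the number of on-site scheduled assessments attended, c = min(m, 2), and u is the number of unscheduled visits. The documents do not give u, so 0, 1 and 4 are assumptions. EOS is taken to fall within the treatment period.

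| EOS timing | u = 0 | u = 1 | u = 4 |
|---|---|---|---|
| Coincides with M6 | 1/1 = 100% | 1/2 = 50.0% | 1/5 = 20.0% |
| After M6, up to M12 | 2/2 = 100% | 2/3 = 66.7% | 2/6 = 33.3% |
| After M12, up to M18 | 2/3 = 66.7% | 2/4 = 50.0% | 2/7 = 28.6% |

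These are shares of assessments, not of patients missed: a patient notable at both an unscheduled visit and M6 is already in the M6 row. With no unscheduled visit and EOS by M12, nothing is missed.

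**The case against.** Most of the opposing case concerns weight, and much of it stands.

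- **The SAP does not depart from the protocol.** A reader might infer that the SAP narrowed the planned analysis. Protocol 9.6 already lists named visits and mentions neither unscheduled visits nor M12; the SAP sentence makes explicit what that list implies.
- **Nothing is hidden or lost.** A reader might infer that symptomatic hypotension could go uncounted. Under Protocol 8.6.1 it is an AE and enters the primary AE table; if treatment-emergent, it can also enter the hypotension group. What remains uncounted is mainly the crossing that meets none of the AE criteria.
- **The listing is complete and short.** With at most 8 patients, hand counting is feasible. The laboratory values behind two of the three dose-adjustment concerns in Protocol 6.4.1 receive a listing only (SAP 2.7.3).
- **The later-visit part is conditional.** No document shows that a patient reached M12. The unscheduled-visit part does not depend on it.
- **An any-time row has its own difficulty.** The treatment period "ends with the date of treatment disposition" (SAP 2.1.1), so an EOS visit may come later. Running the row through EOS without distinction would mix values on and off treatment.

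Restricting by-visit means to scheduled assessments is sound practice and is not in dispute. What survives is that an explicit rule keeps required safety measurements out of every notable-value count, and one row would put that right.

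**Conclusion.** The point holds as a minor gap in the display of supporting safety data. Reading the SAP with Table 1-2, a notable blood pressure or pulse seen only at an unscheduled visit enters no notable-value count; the same applies to a non-EOS on-site visit at M12 or later, if one occurs. The size of any undercount cannot be stated, because the documents give neither the number of unscheduled visits nor the final study length. It may be nil. The percentages in the table above must not be read as a proportion of patients missed. The primary endpoint is not affected, and every recorded value remains visible and flagged in the listing.

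**What to change.** Keep the by-visit rows as they are. Add one row to the notable vital-sign table: distinct patients with at least one notable value at any assessment after first dose and during the treatment period, scheduled or unscheduled, each patient counted once. Identify separately, for example by footnote, any patient whose only notable value is at an EOS visit after the end of the treatment period. Footnote the number of assessments per patient.

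The cost is SAP wording and one table row from data already collected and flagged for the listing. No new data and no protocol amendment are needed. SAP section 4, which now records no changes to the protocol-specified analyses, may need a one-line entry. The downside is that patients with more unscheduled visits have more chances to meet the criteria; the footnote discloses this but does not remove it.

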2.7.4.3 Height and Weight

Descriptive statistics will be provided for test values of weight, height, BMI, age adjusted percentile for weight and height, and z-score for height by visit. For weight, if the timing of EOS and Visit M6 overlaps and two visits are made simultaneously, the data will be used for both EOS and Visit M6. The window of Visit M6 is defined as ±1 month of the scheduled visit date (day183±30).

A listing for these items (i.e. weight, height, BMI, age adjusted percentile for weight and height, and z-score for height) will be provided for all visits including unscheduled assessments.

- Subject ID
- Date of Study Treatment start
- Assessment date (Treatment day, Visit name (Weight only))

Page 19 of 24

Displays the assessment date entered on CRF or imputed, corresponding Treatment day (the number of days from the date of treatment start) and Visit name (Weight only)

- Test name
- Value
- Unit
- Adjusted percentile (Weight, height)
- Z-score (Height only)

BMI will be calculated as weight (kg) / height² (m²) using the collected height and weight at each visit.

Refer to Section 2.3.2 for Z-score and age adjusted percentile.

The SAF will be used for the above analyses.

2.8 Pharmacokinetic endpoints

Not applicable

2.9 PD and PK/PD analyses

Not applicable

2.10 Patient-reported outcomes

Not applicable

2.11 Biomarkers

Not applicable.

2.12 Other Exploratory analyses

Not applicable. There are no exploratory endpoints.

2.13 Interim analysis

Not applicable

3 Sample size calculation

All patients who have completed PANORAMA-HF OLE study and who meet all Inclusion and Exclusion criteria (Section 1.1), are eligible for this extension study.

There is no specific sample size required for the study. A maximum of 8 Japanese patients will be enrolled into the study.

4 Change to protocol specified analyses

None

5 Appendix

5.1 Imputation rules

The missing or partially missing start/end date for AEs and prior/concomitant therapies will be imputed using the Novartis AGB global standard approach.

If the visit date is missing, the scheduled date (per protocol) of the visit will be used.

5.1.1 Study drug

If the study treatment start date is missing, then the planned start date (the date of Visit Day1) will be used. If only the start day is missing (but the month is known), then the start day will be the 1st day of that month, unless the planned date of the Visit Day1 is in the same month, then it will be the planned date of the Visit Day1.

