- 1. Patients who permanently discontinued the study drug treatment during PANORAMA-HF OLE study cannot be enrolled in this study (Section 5.2), however, patients who temporally discontinued the study drug for any reason at the End of Study visit (Visit 599) in PANORAMA-HF OLE study may be enrolled in this study. In this case, the assessments specified for Visit Day1 should be performed at the visit when the study treatment starts. They will have to discontinue the study unless the study treatment starts within 3 months from Visit Day1, and will be considered an early study termination (Section 5.3).
- 2. End of Study (EOS) visit will be completed when marketed product of sacubitril/valsartan pediatric formulation becomes commercially available in Japan, the study treatment is permanently discontinued based on the Investigator's judgement, or participant prematurely withdraws from the study, whichever occurs first.
- 3. Signed informed consent as well as assent at an appropriate age must be obtained prior to participation in the study. Patient Assent document is captured as a source document and is not stored in the clinical database.
- 4. If the trial is extended 1 year or over, height at Visit M12 should be recorded in the electronic Case Report Form (eCRF)
- 5. The data measured at the End of Study visit (Visit 599) in PANORAMA-HF OLE study will be utilized as the data at Visit Day1 for this study.

6. Serum sodium, potassium, creatinine, and estimated Glomerular Filtration Rate (eGFR, modified Schwartz formula) will be measured locally, and recored in the eCRF. Additional laboratory evaluation including hematology and urinalysis may be performed optionally by Investigator's clinical judgement at any visits. There is no local assessment at Visit Day1, but the results of central laboratory at the End of Study visit (Visit 599) in PANORAMA-HF OLE study should be reviewed by the Investigator soon after the results are obtained.

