5.3 Screen failures

Participants or parents/guardians who sign an informed consent form for themselves or for their child, respectively, and who (i.e. the participant) are subsequently found to be ineligible for this study, will be considered a screen failure. The reason for screen failure should be entered on the applicable electronic Case Report Form (eCRF). The baseline characteristics at Visit Day1, demographic information, informed consent, and Inclusion/Exclusion pages must also be completed for screen failure participants. No other data will be entered into the clinical database for participants who are screen failures, unless the participant experienced a serious adverse event (SAE) during the screening phase (see SAE section for reporting details).

Participants or parents/guardians who sign an informed consent for themselves or for their child, respectively, and who are considered eligible but fail to be started on treatment on Visit Day1 for any reason may be enrolled in this study. However, they will have to discontinue the study unless the study treatment starts within 3 months from Visit Day1 and will be considered an early study termination. The reason for early study termination should be captured on the appropriate disposition eCRF at Visit EOS.

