2.4 Treatments (study treatment, rescue medication, concomitant therapies, compliance)

2.4.1 Study treatment / compliance

The study treatment administration is recorded on the Case Report Form (CRF) page: "Dosage Administration Record" using start date, end date, dispensing name of the study treatment and the type of change. Each pair of start date and end date will be considered as a dosing interval, if type of change is recorded as 'Dose interrupted' then this dosing interval will be considered as temporary interruptions.

Duration of exposure to the study treatment will be defined as both the treatment period including temporary interruptions and the treatment period excluding temporary interruptions and summarized for continuous variable.

Dose levels will be summarized for continuous variable by visit, regardless of the pediatric or adult dose level. In addition, the number and percentage of patients for each dose level (Dose level 1 to 4, and No treatment) will be provided by visit.

The dose level for each visit is defined as the dose level of dosing interval with its start date prior to or equal to the scheduled visit date and its end date later than or equal to the scheduled visit date. For EOS visit, actual visit date is used to identify the dose level.

In addition, the following information will be listed.

- Subject ID
- Date of Visit Day1
- Start date (Study day)

Displays the start date entered on CRF or imputed and corresponding Study day (number of days from Visit Day1).

• End date (Study day)

Displays the end date entered on CRF or imputed and corresponding Study day (number of days from Visit Day1).

- Dose Form (Granule/ Liquid/ Tablet)
- Dispensing Name (Dose Level)
- Dose administered
- Unit
- Type of Change (Dose changed/ Dose interrupted/ Dose permanently discontinued)
- Reason for Change (Adverse event/ Disease improvement under study/ Dosing error/ Dispensing error/ Technical problems/ Subject decision/ Guardian decision/ Physician decision/ As per protocol)

The SAF will be used for the above analyses.

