2.5.4 Handling of missing values not related to intercurrent event

The missing value for laboratory assessments, vital signs, height, weight, and other assessments will be not imputed.

The missing or partially missing start/end date for AEs, prior/concomitant therapies, and study drug will be imputed using the Novartis ADaM Governance Board (AGB) global standard approach. Details are provided in Section 5.1.

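### A missing first study-drug start date defaults to Visit Day1 (or the 1st of the month) with no exception for participants the protocol allows to start up to 3 months later

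*SAP*

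**What the plan says.** SAP 2.5.4 sets the scope: "The missing or partially missing start/end date for AEs, prior/concomitant therapies, and study drug will be imputed". For study drug the detail is in SAP 5.1.1, which has two rules.

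- Whole date missing: "If the study treatment start date is missing, then the planned start date (the date of Visit Day1) will be used".
- Day missing, month known: "If only the start day is missing (but the month is known), then the start day will be the 1st day of that month", except that Visit Day1 is used when it lies in that month.

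The protocol does not require drug to start on Visit Day1. Section 5.3 provides that eligible participants who "fail to be started on treatment on Visit Day1 for any reason may be enrolled in this study". Table 1-2 footnote 1 covers patients temporarily off drug at the last visit of the preceding study: "the assessments specified for Visit Day1 should be performed at the visit when the study treatment starts". The same footnote sets the limit: "They will have to discontinue the study unless the study treatment starts within 3 months from Visit Day1".

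The SAP recognises the delayed start elsewhere. In SAP 2.1.1, "The treatment period starts with the date of first administration of study treatment in CLCZ696B2319E2 study", and baseline stays at Visit Day 1 whether or not drug is given that day. SAP 2.7.1 opens the treatment-emergent window at first administration when treatment did not begin at Visit Day 1.

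**The concern.** The default in SAP 5.1.1 is correct for someone who starts on time. For a permitted late starter it replaces a start that took place at a study visit with an earlier date on which the participant was not taking study drug.

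The first-dose date is used in several places:

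- the treatment period and both exposure durations (SAP 2.1.1, 2.4.1);
- Treatment day in the adverse event, medication, laboratory, vital-sign and growth listings;
- the opening of the treatment-emergent window (SAP 2.7.1);
- the reference date for completing partial adverse event start dates (SAP 5.1.2.2), so one imputed date can feed another.

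With at most 8 participants, one affected person is at least 1/8 = 12.5% of any summary. That is the weight of one participant, not the chance that this happens.

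**Working it through.** The plan gives no figure to reproduce: there is no hypothesis and no sample size calculation. The check applies the SAP rules to illustrative records. All dates and end days below are assumptions.

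**Inputs.** Whole-date and day-only rules from SAP 5.1.1; maximum delay of 3 months from Table 1-2 footnote 1, taken as about 91 days; scheduled M3 on study day 91 from SAP 2.1.1.

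**Formulas.** Exposure including interruptions = end date − start date + 1. Excess exposure = true start − imputed start.

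**Worked record.** Visit Day1 is 20 Dec 2023, true start 15 Mar 2024 (within 3 months), end of treatment 20 Sep 2024.

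- Delay: 11 days left in December + 31 + 29 + 15 = 86 days.
- True exposure, 15 Mar to 20 Sep inclusive: 190 days.
- Whole date missing, start set to 20 Dec 2023: 190 + 86 = 276 days; 276/190 = 1.45, an overstatement of 45%.
- Only the day missing, start set to 1 Mar 2024: 14 days too early, so 190 + 14 = 204 days; 204/190 = 1.07.

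**Range, whole date missing (start set to study day 1).**

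| True start day | Treatment ends day | True exposure | Under SAP 5.1.1 | Excess | Ratio |
|---|---|---|---|---|---|
| 31 | 183 | 153 | 183 | 30 | 1.20 |
| 61 | 183 | 123 | 183 | 60 | 1.49 |
| 92 | 183 | 92 | 183 | 91 | 1.99 |
| 31 | 365 | 335 | 365 | 30 | 1.09 |
| 61 | 365 | 305 | 365 | 60 | 1.20 |
| 92 | 365 | 274 | 365 | 91 | 1.33 |

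**Range, day only missing.** The imputed date is never before Visit Day1. Over all start dates tried, the error is at most 30 days.

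**Other outputs, whole date missing.**

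- The Day1 dose level shows a dose where the correct entry is No treatment. M3 is wrong only if the true start falls after day 91.
- Every day of the delay (86 in the worked record, up to about 91) enters the treatment-emergent window of SAP 2.7.1.
- The primary endpoint (SAP 2.5.1) counts adverse events whether treatment-emergent or not, so its counts are the same under either start date.

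**The case against.** The strongest defence is that the case will hardly ever arise. It needs a delayed start and a missing first date in the same participant, out of at most 8. The protocol requires every dosage and change to be entered on the dosage record (6.2.3) and has missing values queried (10.1.5.2). The protocol's own treatment-emergent definition (footnote to 9.6) counts from Visit Day 1, so under that definition off-drug events count anyway. All of this stands, and it keeps the point minor. It does not make the imputed date right. SAP 2.7.1 deliberately uses first administration for late starters. The dosing listing would not necessarily expose the error either: its start-date column reads "Displays the start date entered on CRF or imputed and corresponding Study day (number of days from Visit Day1"), and the columns listed include no flag for an imputed value.

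One could also argue that Visit Day1 moves to the start visit for late starters. Footnote 1 measures the 3-month limit from Visit Day1 to the start of treatment, and SAP 2.1.1 and 2.7.1 keep the two dates apart, so that reading fails.

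A reader might infer more than the documents support:

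- **That a missing start always becomes Visit Day1.** The known-month rule says otherwise.
- **That every restart or dose change is back-dated to Visit Day1.** SAP 5.1.1 equates the missing date with the planned start at Visit Day1, and a restart has no such planned date. The natural reading is the first start only. Later records therefore have no stated rule, rather than a wrong one.
- **That exposure is double-counted.** Take level 4 on days 1–80, an interruption on days 81–100 and level 2 on days 101–183, with the level 2 start back-dated to day 1. Summing dosing records gives 80 + 183 = 263 days instead of 80 + 83 = 163. But SAP 2.4.1 defines exposure as the treatment period with and without interruptions, and 183 − 20 = 163 is correct. The SAP states no summing method. At M3 two records would match, which is an ambiguity rather than a definite wrong level, and the first-dose date and opening of the treatment-emergent window would not move.
- **That the ordering checks for adverse events and concomitant medication show what is missing here.** Those checks compare start and end within one record and do not prevent overlap between successive records.

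**Conclusion.** The point holds for the first dosing record. SAP 5.1.1 gives a wrong first-dose date for a participant whom the protocol allows to start late and whose first start date is missing.

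The error equals the delay, up to about 91 days, when the whole date is missing. It is at most 30 days when only the day is missing. It affects exposure, Treatment day, the Day1 dose level, treatment-emergent status under the SAP definition and the reference date for partial adverse event dates. It does not affect the primary any-event counts.

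The figures rest on assumed dates, on 3 months being about 91 days, and on no interruption record covering the off-drug days before the first dose. Such a record could remove the excess from exposure excluding interruptions. The point is worth correcting because it is cheap, but it does not threaten the study's main result.

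Separately, the SAP has two gaps: no stated rule for a missing start on later dosing records, and no rule in 5.1.1 for the study-drug end dates that 2.5.4 says will be imputed.

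**What to change.** In SAP 5.1.1, state that the rule applies to the first dosing record only. If treatment did not start on Visit Day1, impute the date of the visit at which study drug was started (where the Visit Day1 assessments were done), and never an earlier date. Use Visit Day1 only when drug was started that day. Apply the same floor when only the day is missing.

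Then add two clarifications:

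- **Later dosing records:** a missing start could be set to the day after the previous record's end, where that end is recorded.
- **End dates:** a missing end could be set to the day before the next record's start, where that start is recorded. The SAP also needs a fallback for when both adjoining dates are missing, and for the end of the last record, where the treatment-period end in SAP 2.1.1 is a consistent choice.

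The cost is a few sentences and a small programming change before database lock. No new data are needed, provided the date of the start visit is recorded. The general rule in SAP 5.1, which replaces a missing visit date with the scheduled one, should not be allowed to supply it.
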